7.9.4 Potential surrogate biomarkers

If and only if PFS or OS study results are statistically significant, the CTC status at week 12 alone and in combination with lab parameters will be evaluated as potential surrogate for either PFS or OS using Prentice Criteria (R16-0801). The alpha level will be increased to 20% in order to account for the study size. The following lab parameters and their pairwise combinations will be investigated, if data allows: albumin, alkaline phosphatase, hemoglobin, lactate dehydrogenase. The time points for lab measures will be selected as close as possible

to the CTC status measure and must be on treatment. Details of the analyses are as in R16-0801 and will be described further in Cumulative Statistical Analysis Plan (CSAP).

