5.1.3 Phase II

The primary endpoint for the phase II part of the study is PFS based on investigator assessment.

PFS is defined as the time from randomisation until radiological tumour progression in bone (based on PCWG2 criteria) or soft tissue (based on modified RECIST 1.1) or death from any cause, whichever occurs earlier.

Tumour assessments will be performed at screening, week 8, week 16, week 24 and then every 12 weeks thereafter (more details in CTP Flow Chart).

For each follow-up (FU) imaging time-point an overall tumour response will be determined for soft tissue according to modified RECIST 1.1 (R09-0262 and Appendix 10.4 of the CTP) and for bone according to the prostate cancer clinical trials working group (PCWG2) criteria (R13-1642). The overall tumour response for each imaging time-point according to modified RECIST 1.1 will be selected from the following categories: Complete Response (CR); Partial Response (PR); Stable Disease (SD); No disease (ND); Progressive Disease (PD); Non-CR/Non-PD; Not Evaluable (NE). The overall tumour response for each imaging time-point (if clinically indicated) for bone lesion will be selected from the following categories: Non-progressive disease (Non-PD); Progressive disease (PD); Not Evaluable (NE).

Some patients enter the trial without any target or non-target lesion according to RECIST 1.1. Until new lesions appear and a progression is reported for this patient, the response assessment for such patients will be set to No Disease (ND) (see also Section 5.4.7).

For details on the imaging process and RECIST evaluation, see Section 5.1.2 and Section 10.4 of the CTP.

Derivation of endpoint PFS

Derivations below are described in days. However, the endpoints below will be presented in months in the outputs produced for the Clinical Trial Report (CTR).

For patients with 'event' as an outcome for PFS: (according to modified RECIST version 1.1 or PCWG2)

• PFS [days] = date of outcome - date of randomisation + 1.

For patients with 'censored' as an outcome for PFS: (according to modified RECIST version 1.1 or PCWG2)

• PFS (censored) [days] = date of outcome - date of randomisation + 1.

The censoring rules for PFS (i.e. outcome and date of outcome) are given in Table 5.1.3: 1. Clinical disease progression will not be considered for determination of a PFS event, unless the outcome of the progression is death.

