In case there is no value within this timeframe (day 84 to 92), but the patient discontinued all treatments earlier than day 84, then the End of Treatment (EOT) value should be used. A PSA value will be taken as EOT value if the assessment was performed between the date of discontinuation of the last study medication until 7 days (included) after this date (according to the protocol schedule for the EOT visit (EOTV)).

In case there is no value within this timeframe (day 84 to 92), and the patient did not discontinue all treatments earlier than day 84, no earlier value will be taken as replacement, the assessment will be missing.

PSA response

PSA response is defined as a decline in PSA value >50% (with confirmation at least 3 weeks later) (R13-1642). See Section 5.1.2. for more details.

Changes in CTC response

Changes in CTCs will be evaluated using the following criteria:

- CTC reduction is defined as a decline in CTC value from ≥5 to <5 cells per 7.5mL blood (called "specimen volume" within this section and Section 7.5.2.3) (R14-0865), for at least one post-baseline time-point. Patients with a CTC value <5 cells per 7.5 mL blood at baseline, or with missing baseline value, are not taken into consideration for this endpoint.
- Maximum decline in CTC counts (in number of cells) compared to baseline that occurs at any point after treatment start, defined as the difference (absolute and percentage) between the minimum post-baseline CTC value and the baseline CTC value. Patients with missing baseline value are considered missing for this criterion.
- CTC status at week 12 (≥5 or <5 cells per 7.5mL blood)

Baseline value is the value collected before a patient starts treatment with trial medication. Patients with no post-baseline value are considered as missing for the three criteria.

For the criterion "CTC status at week 12", the nearest assessment to C4V1 (day 85) will be used, with following window:

- A later value, until one week after (day 92), can be used
- An earlier value, after four weeks in trial (day 29), can be used.

In case the patient discontinued the trial before the planned assessment, the EOT assessment will be used for this criterion in case it is the nearest to the target day.

In case it is needed for descriptive tables, multiple entries for one single time point in a patient will be assessed as follows:

- If only one valid value (with acceptable specimen volume or imputable value) is available, this one will be used

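### The week-12 CTC status used in the PFS surrogacy analysis may be sampled at or after the PFS event, which biases the CTC–PFS association

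*SAP*

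**What the plan says.** SAP 7.9.4 states that "the CTC status at week 12 alone and in combination with lab parameters will be evaluated as potential surrogate for either PFS or OS", using the Prentice criteria. The analysis is conditional: "If and only if PFS or OS study results are statistically significant". Its error level is relaxed: "The alpha level will be increased to 20% in order to account for the study size". Further detail is left to a cited paper and to a cumulative SAP, neither of which is among the documents. SAP 7.9 describes the biomarker work as exploratory.

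The two variables are defined elsewhere in the SAP.

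- **PFS** (SAP 5.1.3): "PFS is defined as the time from randomisation until radiological tumour progression in bone" or soft tissue, or death.
- **CTC status at week 12** (SAP 5.2.2.3): "the nearest assessment to C4V1 (day 85) will be used". Values up to day 92 are allowed, and "An earlier value, after four weeks in trial (day 29), can be used". For early stoppers, "In case the patient discontinued the trial before the planned assessment, the EOT assessment will be used for this criterion", provided it is the sample nearest the target day.

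Neither section says that the CTC sample must precede progression. SAP 7.9.4 states no landmark or shifted time origin. It does set timing for the accompanying laboratory values (close to the CTC measure and on treatment), but sets none relative to the PFS event.

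**The concern.** A surrogate has to be measured before the outcome that it is meant to predict. Here the outcome clock starts at randomisation, while the marker may be read as late as day 92, from a patient whose progression is already on record. If progression raises the count, an association between high CTC and short PFS appears even when CTC carries no information about later progression. That association is one of the Prentice criteria, so it would be tested on data in which cause and effect can run backwards for a sizeable minority. The 20% level makes it easier to pass. The analysis would run only after a positive trial, when a surrogacy result is most likely to be used.

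**Working it through.** **1. The schedule.** Cycles last 28 days, so C2D1, C3D1 and C5D1 fall on days 29, 57 and 113. The protocol (Flow Chart; 6.2.2) schedules CTC samples at C1D1, C2D1, C3D1, C5D1, C7D1 and then every 12 weeks. There is none at C4D1 (day 85). C5D1 lies outside the window, so C3D1 is the last scheduled sample inside it. The first on-study scan is at days 49–56, and the EOT visit is within 7 days of stopping. Bone progression first seen at week 8 and later confirmed is dated to the week-8 scan (Protocol 5.1.2.1). A week-8 progressor therefore usually has a PFS date at or before the CTC sample used, whether C3D1 or EOT.

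**2. The plan's own figure.** Protocol 7.6 assumes exponential PFS with λ = ln 2 / median, giving 0.231 (3 months) and 0.151 (4.6 months). With 12 months of accrual and 20% permanently censored, 80 × 0.80 × F(T) = 60 requires F(T) = 0.9375. The protocol's formula gives T = 22.5 months, as in Table 7.6: 3. The other seven rows also reproduce.

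**3. Share with a PFS event by a given day.** With the same model, share = 1 − 0.5^(days / 30.44 / median).

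| Day | Arm B (3 months) | Arm A (4.3–4.6 months) | Patients of 80 |
|---|---|---|---|
| 56 | 35% | 24–26% | about 24 |
| 84 | 47% | 34–36% | about 33 |
| 92 | 50% | 37–39% | about 35 |

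Day 56: 40 × (0.346 + 0.242) = 23.5, or 24.1 with a 4.3-month median in arm A. After 15–20% permanent censoring this is 20.0 to 18.8 events. Scans are at weeks 8 and 16, so progression is not normally recorded between those visits. The day-56 row is the relevant one, and it includes deaths.

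**4. Effect on the CTC–PFS association.** The documents give no CTC rates, so these are assumptions. Let CTC ≥5 occur in 30% of patients regardless of later hazard, but in 50% or 60% of those with an event by day 56, all of whom are taken to supply a sample. In 200,000 simulated patients (medians 3 and 4.6 months) the hazard ratio of CTC status for PFS from randomisation is 1.26 and 1.40; repeat runs gave 1.24–1.38. Measured from day 92 among patients still event-free, it is 0.99–1.02.

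A second illustration uses 80 patients, progression recorded only at scans, 15% censoring and 1,500 runs. CTC ≥5 occurs in 50% without week-8 progression and in 60%, 70% or 80% with it. CTC appears prognostic at the 20% level in 26%, 36% and 52% of runs, against 21–22% from a day-92 landmark.

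**5. Effect on the whole Prentice set.** With the assumptions of the first illustration, the treatment hazard ratio is 0.65 both before and after adjustment for CTC, so CTC captures none of the treatment effect. CTC ≥5 differs between arms by only 2–3 percentage points. In 2,000 simulated trials of 80 patients and 60 events, I required PFS significant at 5%, both CTC criteria at 20%, and an adjusted treatment effect not significant at 5%. All held in about 1% of trials (0.9–1.7% in a repeat run), and in 0.05–0.15% if the last criterion uses 20%.

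**6. The significance condition.** At a two-sided 5% level with 60 events, power = Φ(|ln HR| × √60 / 2 − 1.96). HR 0.65 gives Φ(1.669 − 1.96) = 38%; HR 0.70 gives Φ(1.381 − 1.96) = 28%.

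**The case against.** The strongest reply is that the analysis is exploratory, runs only after a significant PFS or OS result, and leaves its detail to a cited method and a cumulative SAP that may deal with timing. This limits how often the problem arises, and it means that the missing landmark is silence rather than a stated choice. It does not remove the point, because the surrogate variable itself is defined in SAP 5.2.2.3 and that definition admits samples taken after progression.

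Four stronger readings are tempting, and the documents do not support them.

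- **That CTC status would probably be declared a surrogate.** The Prentice criteria also need a treatment effect on the marker and capture of the treatment effect on PFS. The bias supplies neither.
- **That OS is affected in the same way.** No sample can follow death. For OS the question is limited to patients who die before sampling. Removing post-progression samples there would exclude living early progressors informatively.
- **That EOT substitution is the main cause.** It applies only when the EOT sample is nearest day 85. Patients stopping for toxicity, or for clinical progression (not a PFS event under SAP 5.1.3), may give an EOT sample before any event. Some week-8 progressors continue treatment to a confirmatory scan. The scheduled C3D1 sample raises the same problem without EOT.
- **That up to half the patients are affected.** The day-84 and day-92 shares assume continuous detection of progression, which does not fit scans at weeks 8 and 16.

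**Conclusion.** The point holds for PFS and is minor. As defined, week-12 CTC status can be measured at or after the PFS event in up to about 24–35% of patients per arm, roughly 24 of 80 before censoring and less those who died. This rests on exponential PFS at the planning medians. The consequence is bias in one criterion, the CTC–PFS association. Its illustrative size, a hazard ratio of 1.26–1.40 where the truth is 1, depends wholly on assumed CTC rates; the direction follows if progression raises the count. A false surrogacy claim on the full Prentice set remains unlikely, at about 1% of trials under the same assumptions.

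**What to change.** In SAP 7.9.4 or the cumulative SAP, for the PFS surrogacy analysis only:

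- Use the CTC sample nearest day 85, within days 29–92, that was taken before the progression date used for PFS (including a date carried back to the first scan). Apply this to scheduled and EOT samples alike, and set the value to missing if there is none.
- Add a landmark sensitivity analysis, for example at day 92, with PFS measured from that day among patients still event-free.

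Leave the descriptive table under SAP 5.2.2.3 and the use of post-progression samples for OS as they are.

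The change is wording only. Its cost is that some early progressors will contribute a day-29 value or none. The landmark analysis loses patients (about 35 of 80 by day 92 in the exponential model, before censoring; fewer if progression is recorded only at scans), and its comparison of arms is no longer fully randomised. That is why it is proposed as a sensitivity analysis and not as the main one.

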7.9.5 Potential predictive biomarkers

The statistical analyses for potentially predictive biomarkers will be reported outside of the CTR and described in the Translational Medicine and Clinical Pharmacology (TMCP) SAP. This SAP can be found in BIRDS, on substance level, DMS folder, Section 8 and is entitled "8-02-sap-predictive-biomarkers".

7.9.6 Statistical evaluations of pharmacological endpoints

If data are sufficient and calculation of the PK parameters $AUC_{\tau,ss}$ and $C_{max,ss}$ of enzalutamide is feasible, these PK parameters at steady state (ss) in absence and presence of xentuzumab will be compared statistically.

The statistical model used for the analyses will be an ANOVA model on the logarithmic scale and will be based on the PKS. The treatment enzalutamide alone in steady state (PK parameters collected at Day -1/Day 1 in the phase Ib expansion cohort) will be regarded as reference treatment. The treatment enzalutamide + xentuzumab in steady state (PK parameters collected at cycle 2 Day -1/Day 1 in phase Ib expansion cohort) will be referred to as test treatment in this context.

The effect 'subject' will be considered as random, whereas the effect 'treatment' will be considered as fixed for the main analysis. For the sensitivity analysis the effects 'subject' and 'treatment' will be both considered as fixed. The model is described by the following equation:

 $y_{km} = \mu + \tau_k + s_m + \varepsilon_{km},$

where

 y_{km} = logarithm of response (AUC_{τ ,ss} or C_{max,ss}) in subject m receiving treatment k,

 μ = the overall mean,

 τ_k = the k-th treatment effect, k = 1, 2,

 s_m = the effect associated with the m-th subject, m=1,...n,

 ε_{km} = the random error associated with the m-th subject receiving treatment k.

The PK parameters $AUC_{\tau,ss}$ and $C_{max,ss}$ will be log-transformed (natural logarithm) prior to fitting the ANOVA model. The difference between the expected means for the log-transformed PK parameters will be estimated by the difference in the corresponding LS Means (point estimate) and 2-sided 90% confidence intervals based on the t-distribution will be computed. These quantities will then be back-transformed to the original scale to give the point estimator (geometric mean) and interval estimates for the intra-subject ratio of the geometric means for treatments test and reference.

7.9.7 Exposure- and biomarker-efficacy analyses

A Kaplan-Meier analysis (including median, 95% confidence interval, Q1 and Q3 statistics) plus corresponding plot will be conducted for PFS by exposure and selected biomarkers over time (Total and Free IGF's group).

For exposure, the categorized pre-dose concentration at steady-state (>21 days after start of treatment) $C_{pre,ss}$, closest to the efficacy assessment from noncompartmental analysis (see Section 7.6), will be the group determining factor.

For selected biomarkers over time, this analysis will be performed using pre-dose measurements at steady-state accordingly, if feasible.

Cox proportional hazard analysis will additionally be conducted for exposure-efficacy relationship. The validity of the underlying assumptions will be checked.

7.9.8 Immune response (ADA)

The presence of ADAs will be tested at the beginning of each treatment cycle (until cycle 12), at EOT and at the first FU visit. This analysis is done for patients in phase Ib and for patients in the xentuzumab arm in phase II.

The number and percentage of patients with positive and negative results will be presented.

If considered reasonable, the correlation between ADA (positive / negative) and PK and/or PD endpoints may be performed.

If considered reasonable, the correlation between ADA (positive / negative) and disease control (yes / no), and between ADA (positive / negative) and occurrence of acute/non-acute specific adverse events (yes / no) will be studied using a contingency table, along with 95% confidence interval and a Fisher's exact test.

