Preliminary PK interim data from the dose escalation part of both trials indicate that maximum plasma concentrations of BI 836845 are reached at the end of the infusion or shortly thereafter. After reaching the peak, plasma concentrations showed an at least biphasic decay with a terminal half-life of about 6 days. The estimated volume of distribution was about 5.8 L (approx. two times the plasma volume) and the total plasma clearance was about 0.5 mL/min. The incidence of anti-drug antibodies (ADA) was approximately 19% in 1280.1 and 30% in 1280.2. Overall, the ADA-response was weak, dose-independent and in many cases transient and had no impact on PK or PD.

Doc. No.: c02304008-15

Trial Protocol Version 12

Page 26 of 241

Proprietary confidential information. © 2022 Boehringer Ingelheim International GmbH or one or more of its affiliated companies. All rights reserved.

No deviations from dose-proportional pharmacokinetics have been observed in the dose range analysed (10-1050 mg q1w in 1280.1 and 10-3600 mg q3w in 1280.2). Steady state plasma concentrations of BI 836845 were achieved after 5-7 weeks. Repeated weekly dosing resulted in about 1.5 fold accumulation of BI 836845 plasma concentration at steady state, while only limited accumulation was observed after repeated infusions every three weeks.

It is known that humanised IgGs like BI 836845 are mainly cleared by catabolism. This mechanism of clearance is not shared or overlapping with the clearance mechanism for small molecules. Thus, BI 836845 is not predicted to directly affect the hepatic, renal, or biliary elimination of small molecules. Furthermore, BI 836845 is not targeting cytokines, and mAbs targeting upstream IGFs have not been related to modulation of CYP450 isozymes or drug transporters (P13-02270). Hence, the potential of BI 836845 to alter the pharmacokinetics of co-medication is considered low.

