3.3 SELECTION OF TRIAL POPULATION

A total of up to approximately 120 patients may be recruited into the study. Approximately 9-12 patients will be entered into the phase Ib tolerability and safety phase of the study (escalation part) to ensure the safety of the combination therapy and determine the MTD and/or recommended phase II dose (RP2D). For the exploratory expansion cohort approximately 25 patients will be treated with BI 836845 at the MTD, and/or recommended phase II dose (RP2D) in combination with enzalutamide.

In phase II of the study, 80 patients will be randomised onto one of the two study arms, with 40 patients randomised to each arm (Arm A=40, Arm B=40).

The Phase Ib escalation part of the study will be performed in 4 or more centres. The Phase Ib expansion part of the study will be performed in 8 or more centres. The Phase II of the study will be performed in 25-30 centres globally.

A log of all patients included into the study (i.e. having given informed consent) will be maintained in the ISF at the investigational site irrespective of whether they have been treated with investigational drug or not.

Page 39 of 241

Proprietary confidential information. © 2022 Boehringer Ingelheim International GmbH or one or more of its affiliated companies. All rights reserved.

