7.9 STATISTICAL BIOMARKER AND PK/PD ANALYSES

The biomarkers collected in different parts of the trial will be analyzed and reported separately for each part of the trial.

As statistical biomarker analyses are purely exploratory, there will be no strict error control in a confirmatory sense.

If data is available, the following biomarkers will be evaluated and reported in the CTR:

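### The planned table of ADA status by disease control can show a spurious association in favour of ADA-positive patients if any positive sample counts, because ADA sampling lasts only as long as treatment does

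*SAP*

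**What the plan says.** SAP 7.9.8 states that ADA "will be tested at the beginning of each treatment cycle (until cycle 12), at EOT and at the first FU visit", and that "This analysis is done for patients in phase Ib and for patients in the xentuzumab arm in phase II". If considered reasonable, "the correlation between ADA (positive / negative) and disease control (yes / no" and that between ADA and specific adverse events (also yes/no) "will be studied using a contingency table, along with 95% confidence interval" and a Fisher's exact test. ADA may also be related to PK or PD endpoints.

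Under Protocol 3.1, patients stay on treatment until progression, undue toxicity or another reason to stop. SAP 7.9 calls the biomarker analyses purely exploratory and says that biomarkers "will be analyzed and reported separately for each part of the trial". Protocol 3.3 sets the phase II size, "with 40 patients randomised to each arm (Arm A=40, Arm B=40" in its words. On background rates, Protocol 1.2.1 reports: "The incidence of anti-drug antibodies (ADA) was approximately 19% in 1280.1 and 30% in 1280.2". It adds that the ADA response was weak, often transient, and without effect on PK or PD.

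SAP 4.1 adds disease control as a further endpoint. Its definition is not in the available text, and neither is a rule for reducing serial ADA results to one positive/negative status. SAP 7.9.8 as shown has no landmark, no common sampling window, no time-dependent term and no adjustment for exposure.

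**The concern.** A yes/no ADA status compared across a yes/no outcome assumes that both outcome groups had the same chance to be found positive. Here they do not. A patient who progresses at the first scan leaves with few samples and little time to seroconvert; a patient with disease control keeps being exposed and tested. If one positive sample at any time makes a patient ADA-positive, longer disease control by itself raises the positive rate. This is the familiar immortal-time problem.

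What is at stake is the reading of immunogenicity. The artefact runs towards ADA-positive patients appearing to do better on disease control, the opposite of the loss of activity that one would want this table to detect. In the adverse-event table, longer exposure can raise both ADA positivity and the chance of an event.

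**Working it through.** The documents give no error rate or power for this table, so there is no plan figure to reproduce. The check is a simulation in which ADA has no relation to progression.

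**Inputs from the documents**
- Phase II combination arm, n = 40 (Protocol 3.3).
- Median PFS 4.6 months in that arm (Protocol 7.6), exponential: ln 2 / 4.6 = 0.151 per month, which matches the protocol's own rate.
- Scans at weeks 8, 16 and 24, then every 12 weeks (SAP 5.1.3); 28-day cycles.
- ADA samples as in SAP 7.9.8.
- Overall ADA incidence 19% or 30% (Protocol 1.2.1, two monotherapy trials).

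**Assumptions not in the documents**
- Any positive sample makes the patient positive.
- Disease control means no progression at the week 8, 16 or 24 scan (all three shown).
- Treatment stops at the scan that detects progression.
- Two-sided 0.05 is a benchmark only.
- Three models of ADA timing: (a) a constant chance of a positive result per sample; (b) a constant seroconversion hazard; (c) all seroconversion within 8 weeks, persisting.

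**Sampling opportunity.** A patient stopped at the week 8 scan has post-baseline samples at C2D1, end of treatment and first follow-up: 3. A patient treated beyond the start of cycle 12 has C2D1 to C12D1 plus those two: 11 + 2 = 13. Simulated mean samples with versus without disease control are 9.4 v 3.0 (week 8), 10.8 v 3.9 (week 16) and 12.0 v 4.6 (week 24).

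**Share with disease control.** exp(−0.151 × t), with week 8 = 56/30.44 = 1.84 months, gives 0.757; weeks 16 and 24 give 0.574 and 0.435. The simulation agrees.

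**Results under no ADA effect, n = 40, model (b)**

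| Disease control judged at | Incidence | Positive, control v no control | Odds ratio | Fisher p<0.05 |
|---|---|---|---|---|
| Week 8 | 19% | 0.228 v 0.076 | 3.6 | 5% |
| Week 8 | 30% | 0.356 v 0.130 | 3.7 | 16% |
| Week 16 | 19% | 0.264 v 0.092 | 3.5 | 16% |
| Week 16 | 30% | 0.407 v 0.158 | 3.7 | 32% |
| Week 24 | 19% | 0.295 v 0.106 | 3.5 | 24% |
| Week 24 | 30% | 0.448 v 0.177 | 3.8 | 38% |

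The odds ratio at week 16 and 19% is, for example, (0.264/0.736) / (0.092/0.908) = 3.5. Model (a) is slightly milder: odds ratio 2.9 to 3.3 at weeks 16 and 24, with rejection of 14–27% and 19–29%. A repeat of model (b) gave 5–15%, 16–31% and 24–39% for the three definitions. Over both models and the repeat, the ranges are about 4–16% (week 8), 14–32% (week 16) and 19–39% (week 24).

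**Unbiased comparators.** Model (c) gives an odds ratio of 1.0 and rejection of 2–3%, the true size of Fisher's test here. With ADA status taken only from samples up to C3D1, models (a) and (b) give equal positive rates in the two groups (about 4–9%), an odds ratio of about 1.0 and rejection of 0.5–1.6%.

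The adverse-event table was not simulated.

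**The case against.** The strongest reply is that the plan never says a patient counts as positive on any single sample. SAP 5.3, 5.4 and 7.6 are not in the public text, and a rule for serial ADA results may sit there with the disease-control definition. Elsewhere the SAP does fix a window when it reduces serial data to a status, as for CTC status at week 12. This stands: any-time positive is the natural reading of a per-patient positive/negative count from repeated tests, but it is a reading.

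The size also depends on unknowns. No document gives the timing of ADA onset; if it is all early, there is no bias. With disease control judged at week 8 and 19% incidence, rejection is only 4–5%, within a nominal 5%, though about twice the test's unbiased size.

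The analysis is conditional and exploratory, and monotherapy data showed no effect of ADA on PK or PD. That excuses loose error control. It does not make a biased estimate informative, and judging an analysis reasonable is no stated check against this bias.

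A reader might go further and infer that the table must favour ADA-positive patients, or that the safety table is biased in the same way. The documents support neither. In the adverse-event table, longer exposure raises both margins, whereas an event that ends treatment early shortens sampling and pulls the other way. That a real loss of activity would be masked is plausible from the direction of the artefact, but was not tested.

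**Conclusion.** The point holds in conditional form. If any positive sample defines ADA status, and seroconversion or intermittent positivity continues over time, the disease-control table compares groups with unequal opportunity to test positive. It can then produce a null odds ratio of about 3 to 4 in favour of ADA-positive patients. At n = 40 the false-positive rate ranges from close to nominal (week 8 definition, 19% incidence) to over a third (week 24 definition, 30% incidence). These figures rest on the exponential PFS assumption, the monotherapy ADA rates and the disease-control definitions tried. They would not apply if all seroconversion fell within 8 weeks, or if an unseen section already fixes a common window. For adverse events, only the unequal exposure is established, not the direction of its effect. This is an interpretability problem in a secondary exploratory analysis.

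**What to change.** In SAP 7.9.8:

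1. State, or cross-reference, how serial ADA results become one status, including how transient positives are handled.
2. For efficacy, enter ADA as a time-dependent covariate in the PFS Cox model, with each patient negative until the first positive sample.
3. For safety, count adverse events by onset after first positive ADA, with exposure time accounted for (for example, rates per patient-time before and after).
4. If a 2×2 table is kept, define ADA status from a common window, such as samples up to C3D1, among patients alive and progression-free then, and relate it to later disease control. Do not interpret an any-time-positive table.

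The cost is SAP wording; the data are the same. The landmark table has a real price. With about 0.757 × 40 = 30 patients progression-free at week 8 and 4–9% positive, it would hold roughly 1 to 3 positive patients under continuing seroconversion. It also omits early leavers, late seroconverters and adverse events before the landmark. The time-dependent model should therefore be the main analysis and the table at most a supplement.
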